4.3 Sample Size

[figure not shown]
The co-primary endpoints will be tested first for the combined high and standard adalimumab dose groups versus external placebo and then individual dose groups versus external placebo separately, controlling the familywise Type I error (multiple significance level) of 5% in a strong sense. For each individual test the nominal power will be calculated.

Assuming a 48% remission rate per PMS at Week 8 for the combined standard and high adalimumab induction dose groups and a remission rate per PMS of 19.83% for external placebo, a total of 77 subjects (presuming HD:SD = 46:31) in ITT-E population (see Section 5.1) provides at least 99% power for a one-sample two-sided Chi-square test using a significance level of 5%.

Assuming a 36% remission rate per Mayo Score at Week 52 for the combined standard and high maintenance dose groups and a remission rate per Mayo Score of 18.37% for external placebo, a total of 57 subjects (presuming HD:SD = 28:29) in the combined adalimumab maintenance dose groups in mITT-E population (see Section 5.1) provide 88% power for a one-sample two-sided Chi-square test using a significance level of 5%.

Assuming that the high adalimumab dose regimen is associated with higher efficacy than the standard adalimumab dose regimen and assuming a 52% remission rate per PMS at Week 8 for the high adalimumab induction dose group and a remission rate per PMS of 19.83% for external placebo, 46 subjects in the high adalimumab induction dose group of ITT-E population provide at least 99% power for a one-sample two-sided Chi-square test using a significance level of 4.95%.

Assuming a 41% remission rate per Mayo Score at Week 52 for the high adalimumab maintenance dose group and a remission rate per Mayo Score of 18.37% for external placebo, a total of 28 subjects in the high adalimumab maintenance dose group of the mITT-E population provide at least 80% power for a one-sample two-sided Chi-square test using a significance level of 4.95%.

Based on the assumption of a 75% response rate at Week 8, 93 subjects were to be included in the study (presuming 12 internal placebo subjects in the maintenance part of the study who were included prior to Amendment 4) to ensure 57 subjects in the combined adalimumab maintenance dose groups.

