Treatment-emergent Adverse Events (AEs) and serious adverse events (SAEs) will be summarized by system organ class (SOC) and preferred term (PT) according to the Medical Dictionary for Regulatory Activities (MedDRA) AE coding dictionary. A summary of AEs by severity and relationship to study drug will be performed. Changes in laboratory and vital sign data will be summarized using descriptive statistics. Shift tables will be provided.

Statistical Methods (Continued):

Sample Size:

The co-primary endpoints will be tested first for the combined high and standard adalimumab dose groups versus external placebo and then for the individual dose groups versus external placebo separately, controlling the multiple significance level of 5%. For each individual test the nominal power is calculated.

Assuming a 48% remission rate per PMS at Week 8 for the combined standard and high adalimumab induction dose groups and a remission rate per PMS of 19.83% for external placebo, a total of 77 subjects (high:standard = 46:31) in ITT-E population provides at least 99% power for a one sample two-sided Chi-square test using a significance level of 5%.

Assuming a 36% remission rate per Mayo Score at Week 52 for the combined standard and high maintenance dose groups and a remission rate per Mayo Score of 18.37% for external placebo, a total of 57 subjects in the combined adalimumab maintenance dose groups in mITT population (e.g., high:standard = 28:29) provide 88% power for a one sample two-sided Chi-square test using a significance level of 5%.

Assuming that the high adalimumab dose regimen is associated with higher efficacy than the standard adalimumab dose regimen, assuming a 52% remission rate per PMS at Week 8 for the high adalimumab induction dose group and a remission rate per PMS of 19.83% for external placebo, 46 subjects in the high adalimumab induction dose group of ITT-E population provide at least 99% power for a one sample two-sided Chi-square test using a significance level of 4.95%.

Assuming a 41% remission rate per Mayo Score at Week 52 for the high adalimumab maintenance dose group and a remission rate per Mayo Score of 18.37% for external placebo, a total of 28 subjects in the high adalimumab maintenance dose group of mITT population provide at least 80% power for a one sample two-sided Chi-square test using a significance level of 4.95%.

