8.2 Determination of Sample Size

The co-primary endpoints will be tested first for the combined high and standard adalimumab dose groups versus external placebo and then individual dose groups versus external placebo separately, controlling the multiple significance level of 5%. For each individual test the nominal power is calculated.

Assuming a 48% remission rate per PMS at Week 8 for the combined standard and high adalimumab induction dose groups and a remission rate per PMS of 19.83% for external placebo, a total of 77 subjects (high:standard = 46:31) in ITT-E population provides at least 99% power for a one sample two-sided Chi-square test using a significance level of 5%.

Assuming a 36% remission rate per Mayo Score at Week 52 for the combined standard and high maintenance dose groups and a remission rate per Mayo Score of 18.37% for external placebo, a total of 57 subjects in the combined adalimumab maintenance dose groups in mITT population (e.g., high:standard = 28:29) provide 88% power for a one sample two-sided Chi-square test using a significance level of 5%.

Assuming that the high adalimumab dose regimen is associated with higher efficacy than the standard adalimumab dose regimen and assuming a 52% remission rate per PMS at Week 8 for the high adalimumab induction dose group and a remission rate per PMS of

19.83% for external placebo, 46 subjects in the high adalimumab induction dose group of ITT-E population provide at least 99% power for a one sample two-sided Chi-square test using a significance level of 4.95%.

Assuming a 41% remission rate per Mayo Score at Week 52 for the high adalimumab maintenance dose groups and a remission rate per Mayo Score of 18.37% for external placebo, a total of 28 subjects in the high adalimumab maintenance dose group of the mITT population provide at least 80% power for a one sample two-sided Chi-square test using a significance level of 4.95%.

Based on the assumption of a 75% response rate at Week 8, 93 subjects will have to be included in the study (including ~12 internal placebo subjects in the maintenance part of the study who were included prior to Amendment 4) to ensure 57 subjects in the combined adalimumab maintenance dose groups.

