- Determine if a subject missed work (based on Q2) in order to analyze the proportion of subjects who missed work:
 - Create a binary (YES or NO) "missed work" variable.
 - A subject will be considered as yes to missed work if Q2 is greater than 0.
 - If Q2 = missing, then MISSED WORK = missing.
 - \circ If Q2 > 0, then MISSED WORK = YES
 - \circ If Q2 = 0, then MISSED WORK = NO
 - Therefore, the proportion of subjects who missed work will be counted based on the number of subjects with MISSED WORK = YES.

Partial Study Dates: If the day and/or month are missing, the following conventions will be used to impute the missing visit (or assessment) dates other than the dosing dates:

- 01 for missing start day,
- End of month for missing end day,

- January 1st will be used for a missing start month,
- December 31st for missing end month.

In case of partially missing AE start and stop dates, the dates will be imputed by comparing to first dose date of study medication so that the corresponding AEs will be made treatment-emergent whenever possible.

In case of missing or partially missing study drug dosing dates, the dates will not be imputed. Subjects will be considered as not receiving dose on that date.

[figure not shown]
Rounding

Rounding will be performed only for presentation of results. No rounding will be performed before or during analyses/calculations. The ROUND function of SAS will be used to round results for presentation.

The mean and median will be rounded for presentation to one decimal more than the data were entered into the database. For example, mean systolic blood pressure will be presented to one decimal place (125.2 mmHg) when it is recorded to integer level in the database (110 mmHg). The standard deviation will be rounded to two decimal places more than the data were entered into the database (e.g., 25.31 mmHg for systolic blood pressure). The minimum and maximum values will be presented as entered into the database.

Probabilities will be rounded to three decimal places before assignment of statistical significance and will be presented in rounded format. Probabilities that round to zero or are reported by SAS as zero will be presented as '< 0.001.'

Percentages will be rounded for presentation to one decimal place; e.g., the proportion 0.1244 will be reported in percent as 12.4%.

Score Definitions

1. Mayo Score and Component Scores

 Table 2.
 Definition of Mayo Score and Component Scores

Term	Definition

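### The 80% power floor for 28 high-dose subjects at Week 52 is a large-sample value (exact 77.5%), and SAP 6.0 contradicts itself on rounding p-values

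*SAP*

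**What the plan says.** **Power.** SAP 4.3 states that "a total of 28 subjects in the high adalimumab maintenance dose group of the mITT-E population provide at least 80% power", with 41% assumed on the high dose, 18.37% for external placebo and a 4.95% level. Protocol 8.2 makes the same claim ("provide at least 80% power for a one sample two-sided Chi-square test using a significance level of 4.95" per cent), and so does the synopsis in Protocol 1.2 ("28 subjects in the high adalimumab maintenance dose group of mITT population provide at least 80% power"). For the two doses combined (57 subjects, 36% against 18.37%), SAP 4.3 says they "provide 88% power for a one-sample two-sided Chi-square test using a significance level of 5" per cent. The split between doses is only assumed: "presuming HD:SD = 28:29" in the SAP and "e.g., high:standard = 28:29" in the protocol. SAP 4.3 adds: "For each individual test the nominal power will be calculated". Neither document says whether the figures are large-sample or exact.

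**Rounding.** SAP 6.0, under Rounding, begins: "Rounding will be performed only for presentation of results". Its next sentence rules out rounding before or during any analysis or calculation. Further down the same subsection, p-values are to be rounded to three decimals before statistical significance is assigned. The subsection does not say whether a result is significant at < or at ≤ the level.

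**The concern.** A claim of *at least* 80% sets a lower bound for a named test at a named n. With 28 subjects the test can reject only at whole counts, so its true power may differ from the smooth formula. Of the four tests for which power is given, this one has the lowest stated figure, so it has the least room for that difference.

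The rounding sentences matter because assigning significance is a decision, not presentation. Two programmers following different sentences of SAP 6.0 could treat a p-value close to 0.05 differently in a confirmatory test.

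**Working it through.** **Inputs** (SAP 4.3, Protocol 8.2): p0 = 0.1837; p1 = 0.41 with n = 28 and α = 0.0495 (high dose); p1 = 0.36 with n = 57 and α = 0.05 (combined). Test: one-sample two-sided chi-square, no continuity correction mentioned.

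**Step 1: reproduce the stated figures.** Large-sample power = Φ{[(p1 − p0) − z·√(p0(1−p0)/n)] / √(p1(1−p1)/n)}.

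- High dose: z = 1.9643; null SE = √(0.1837 × 0.8163/28) = 0.0732; alternative SE = √(0.41 × 0.59/28) = 0.0929. Φ[(0.2263 − 0.1437)/0.0929] = Φ(0.888) = 81.3%. At least 80% reproduces.
- Combined: z = 1.9600; SEs 0.0513 and 0.0636. Φ[(0.1763 − 0.1005)/0.0636] = Φ(1.192) = 88.3%. The stated 88% reproduces.

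**Step 2: exact power of the named test.** For each count x, z = (x − n·p0)/√(n·p0(1−p0)).

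- n = 28: 9/28 gives z = 1.882, p = 0.0598 (no rejection); 10/28 gives z = 2.370, p = 0.0178 (rejection). In the lower tail, 1/28 gives p = 0.0432. The test rejects at x ≥ 10 or x ≤ 1. Under Binomial(28, 0.41) this has probability 77.5%, with a negligible lower-tail part. Under Binomial(28, 0.1837) the two-sided size is 4.8% (upper tail 2.3%). The upper cut-off, and so the 77.5%, is the same at α = 0.05, with a continuity correction, or with an exact binomial test.
- n = 57: 16/57 gives p = 0.0586 and 17/57 gives p = 0.0255. Exact power is 86.7% and two-sided size 3.8%.
- The Week 8 claims of at least 99% hold exactly: 99.96% at n = 77 and 99.7% at n = 46.

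**Step 3: neighbouring n, with size beside power.**

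| Test | n | First rejecting count | Exact power | Exact two-sided size |
|---|---|---|---|---|
| High dose | 26 | 9 | 80.4% | 4.2% |
| High dose | 27 | 9 | 84.3% | 7.6% |
| High dose | 28 | 10 | 77.5% | 4.8% |
| High dose | 29 | 10 | 81.6% | 5.0% |
| High dose | 30 | 10 | 85.1% | 5.4% |
| Combined | 56 | 16 | 90.5% | 5.7% |
| Combined | 57 | 17 | 86.7% | 3.8% |
| Combined | 58 | 17 | 88.6% | 4.1% |

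**Step 4: average over realised n.** Assumption: Week 8 responders follow Binomial(93, 0.75), less 12 on placebo, the rest split evenly (odd totals either way with probability one half). Average exact power is 82.4% for the high dose and 88.7% for the combined test.

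**Step 5: rounding.** Under ≤, p-values between 0.0500 and 0.0505 become 0.050 and pass a 5% test. Under <, p-values from 0.0495 up to 0.0500 become 0.050 and fail it. At 4.95% nothing moves, because 0.0495 is itself a rounding boundary; the same is true of 0.0005.

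- At the planned combined sizes the p-values on either side of the cut-off are far from 0.05: Week 8 remission 22/77 p = 0.0544, 23/77 p = 0.0271; Week 52 remission as in Step 2; response 21/57 p = 0.0648, 22/57 p = 0.0317; mucosal healing 18/57 p = 0.0819, 19/57 p = 0.0395.
- For the two combined co-primary tests, no efficacy-direction count has a p-value from 0.0495 to 0.0505 at any n from 20 to 93.
- Isolated cases exist for secondary endpoints at other n: response 22/59 against 26.10% (p = 0.0504) and steroid-free remission 14/37 against 24.08% (p = 0.0503). They change only under ≤ and only if tested at a full 5%.

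**The case against.** The strongest reply on power is that nothing is miscalculated. The chi-square test is itself asymptotic, both documents call the figures nominal, and neither promises exact power. The shortfall belongs to one n within a presumed split; one subject either way takes exact power above 80%, and the average is 82.4%. The sample size is already final, so relabelling alters nothing in the conduct of the trial.

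Most of this stands. What remains is that *nominal* is attached to each individual test in a multiple procedure and does not tell the reader that the power is asymptotic, while *at least* states a bound that the named test misses at the stated n.

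A reader might infer that 27 would have been a better size than 28. It would not: at n = 27 the higher power comes with a two-sided size of 7.6% against a nominal 4.95%. Exact powers at neighbouring n should not be shown without exact size.

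On rounding, the reply is that no decision changes at the levels and sizes the text gives. That is correct and limits the urgency, but two conflicting sentences still govern a confirmatory decision.

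**Conclusion.** Both points hold and both are minor. The 80% floor is a correct large-sample value (81.3%) that the named test does not deliver at n = 28, where exact power is 77.5%, or 2.5 points short. The combined figure is 1.3 points high (86.7% against 88%). The exact powers rest only on the documents' own rates, sizes and levels; the 82.4% average rests on the binomial-responder and even-split assumption.

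Three stronger readings are not supported. A reader might infer an arithmetic error, but the stated figures reproduce. A reader might infer that the trial is underpowered and needs more subjects, but 77.5% is a local trough. A reader might infer that rounding breaks 5% familywise control. The secondary-endpoint cases need the ≤ rule and a full 5% local level; the local levels are in a graph not reproduced in the text available here, and the visible text does not establish them. Nor are 0.0495 and 0.0005 beyond the reach of three-decimal p-values, since both are rounding boundaries.

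**What to change.** **SAP 4.3, Protocol 8.2 and the synopsis:** restate the Week 52 powers as large-sample approximations (about 81% and 88%). Beside them give exact power at the planned n (77.5% and 86.7%) with exact two-sided size (4.8% and 3.8%). If neighbouring n are listed, show size next to power, for example n = 27 (84.3%, 7.6%) and n = 56 (90.5%, 5.7%).

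**SAP 6.0:** delete the rule that rounds p-values before significance is assigned. State that unrounded p-values are compared with the assigned local level, and whether the rule is < or ≤. Keep three-decimal rounding for display.

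The cost is wording only; the design, test, levels and sample size do not change.

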4.4 Interim Analysis

No interim analyses will be conducted.

5.0 Analysis Populations

5.1 Definition for Analysis Populations

Seven study populations will be used for analyses in this study. These are:

[figure not shown]
Intent-To-Treat (ITT) population: The ITT population includes all subjects who received at least one dose of the study medication during induction period. ITT subjects will be analyzed as randomized/enrolled.

ITT-E population: The ITT-E population will be a subpopulation of the ITT population, where subjects who have received open-label high induction dose will be excluded. The ITT-E is the primary population for the confirmatory induction period efficacy analyses.

Modified ITT (mITT) population: The mITT population consists of all Week 8 PMS responders who were randomized at Week 8 and received at least one dose of the study medication during maintenance period. mITT subjects will be analyzed as randomized at the beginning of maintenance phase.

mITT-E population: The mITT-E population will be a subpopulation of the mITT population, where subjects who have received Placebo will be excluded. The mITT-E is the primary population for the confirmatory maintenance period efficacy analyses.

Re-Randomized (RR) population: Consists of all subjects who were re-randomized due to a disease flare and received at least one dose of the study medication after the re-

randomization. RR subjects will be analyzed as randomized at the beginning of maintenance phase.

[figure not shown]
Safety population: Includes all subjects who received at least one dose of the study drug. The safety population will be analyzed (separately for induction and maintenance phase) as treated, according to treatment the subject actually received. The safety population will be used for safety analyses.

Per Protocol (PP) populations: The PP populations will only be used for sensitivity analyses of the co-primary and ranked secondary endpoints.

- The I-PP population is a subset of the ITT-E population/mITT-E population consisting of subjects without major protocol deviations within the induction period.
- The M-PP population is a subset of the mITT-E population consisting of subjects without major protocol deviations throughout the study.

The following treatment groups will be distinguished for ITT [ITT-E will comprise only I-HD and I-SD], mITT [mITT-E will comprise only M-HD and M-SD], safety and RR population:

- a. Randomized high induction dose (I-HD): randomized prior to Protocol Amendment 4 to adalimumab 2.4 mg/kg (maximum dose of 160 mg) at Baseline and at Week 1, adalimumab 1.2 mg/kg (maximum dose of 80 mg) at Week 2, followed by a dose of 0.6 mg/kg (maximum dose of 40 mg) at Weeks 4 and 6.
- b. Randomized standard induction dose (I-SD): randomized prior to Protocol Amendment 4 to adalimumab 2.4 mg/kg (maximum dose of 160 mg) at Baseline and matching placebo at Week 1, adalimumab 1.2 mg/kg (maximum dose of 80 mg) at Week 2, followed by a dose of 0.6 mg/kg (maximum dose of 40 mg) at Weeks 4 and 6.
- c. Open-label high induction dose (I-HD-OL): enrolled under Protocol Amendment 4 or later versions with adalimumab 2.4 mg/kg (maximum dose of

[figure not shown]

160 mg) at Baseline and at Week 1, adalimumab 1.2 mg/kg (maximum dose of 80 mg) at Week 2, followed by a dose of 0.6 mg/kg (maximum dose of 40 mg) at Weeks 4 and 6.

- d. Double-blind High maintenance dose (M-HD): adalimumab 0.6 mg/kg (maximum dose of 40 mg) ew
- e. Double-blind Standard maintenance dose (M-SD): adalimumab 0.6 mg/kg (maximum dose of 40 mg) eow with matching placebo on the alternate week
- f. Double-blind Placebo (M-PL): placebo

Additionally for RR population:

- M-HD with re-induction dose (F-REIND): Subjects randomized to M-HD and (due to 1st disease flare) re-randomized to receive re-induction dose (2.4 mg/kg [maximum of 160 mg]) at the visit, then resumed to receiving the high dose (0.6 mg/kg [maximum of 40 mg]) ew.
- M-HD without re-induction dose (F-NREIND): Subjects randomized to M-HD and (due to 1st disease flare) re-randomized to maintain the high dose (0.6 mg/kg [maximum of 40 mg]) ew.
- M-SD with re-induction dose (F-REIND): Subjects randomized to M-SD and (due to 1st disease flare) re-randomized to receive re-induction dose (2.4 mg/kg [maximum of 160 mg]) at the visit, then resumed to receiving the standard dose (0.6 mg/kg [maximum of 40 mg]) eow.
- M-SD without re-induction dose (F-NREIND): Subjects randomized to M-SD and (due to 1st disease flare) re-randomized to receive one dose of 0.6 mg/kg [maximum of 40 mg] and then maintained the standard dose (0.6 mg/kg [maximum of 40 mg]) eow.
- M-PL with re-induction dose (F-REIND): Subjects randomized to M-PL and (due to 1st disease flare) re-randomized to receive re-induction dose (2.4 mg/kg [maximum of 160 mg]) at the visit. Afterwards, subjects were to receive the standard dose (0.6 mg/kg [maximum of 40 mg]) eow.
- M-PL without re-induction dose (F-NREIND): Subjects randomized to M-PL and (due to 1st disease flare) re-randomized to receive 0.6 mg/kg [maximum of

40 mg] at the visit. Afterwards, subjects were to receive the standard dose (0.6 mg/kg [maximum of 40 mg]) eow.

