7.0 Protocol Deviations

AbbVie does not allow intentional/prospective deviations from the protocol. The principal investigator is responsible for complying with all protocol requirements, and applicable global and local laws regarding protocol deviations. If a protocol deviation occurs (or is identified) after a subject has been enrolled, the principal investigator is responsible for notifying Independent Ethics Committee (IEC)/Independent Review Board (IRB) regulatory authorities (as applicable), and the following AbbVie Representative:

[REDACTED], MD
Immunology Development
AbbVie Deutschland GmbH & Co. KG
[name]
[REDACTED]
[name]
Germany

Telephone Contact Information:

Phone: [REDACTED]

Fax: [REDACTED]

Cell: [REDACTED]

Email: [REDACTED]

For the purposes of this protocol, reportable deviations are defined as:

- Subject entered into the study even though she/he did not satisfy entry criteria
- Subject who developed withdrawal criteria during the study and was not withdrawn
- Subject who received wrong treatment or incorrect dose
- Subject who received excluded or prohibited concomitant treatment

Such contact must be made as soon as possible to permit a review by AbbVie to determine the impact of the deviation on the subject and/or the study.

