8.1.4 Statistical Analyses of Efficacy

The efficacy analysis will be performed in the ITT-E population for the Week 8 efficacy endpoints and in the mITT population for the Week 52 efficacy endpoints. Non-responder imputation (NRI) will be used to impute missing values for binary efficacy endpoints. Subjects who do not complete the induction period or who receive rescue therapy during the maintenance period will be considered as failures from that time point forward. Both LOCF and observed case analyses will be performed for continuous efficacy endpoints.

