Subjects were expected to remain on blinded therapy throughout the 44-week maintenance period. However, subjects with a disease flare could be re-randomized to receive blinded treatment at or after Week 12 (Figure 3 and Figure 4). If subjects continued to meet the definition of disease flare (2nd time) following at least a 4-week course of blinded therapy since the subjects have been re-randomized for disease flare, they could switch to receive open label therapy every week at the dose 0.6 mg/kg [maximum of 40 mg]. If subjects continued to meet the definition of disease flare (3rd time) following a 4-week course of open-label adalimumab every week at the dose 0.6 mg/kg [maximum of 40 mg], they could be switched to receive adalimumab open-label 40 mg ew (maximum dose, not weight-based). More details are described in the protocol Section 5.1.

Subjects with persistent disease flare while on adalimumab 40 mg ew (max dose) could be withdrawn from the study at the investigator's discretion.

During the open-label rescue therapy, subjects who were responders and have been in remission for at least 8 consecutive weeks (PMS \leq 2 with no individual subscore > 1) could have their dosage decreased from ew to eow. If subjects demonstrated disease flare after dose de-escalation, subjects also had an opportunity to re-escalate their dose back to adalimumab ew dosing.

For subjects who met the criteria for dose change, blood samples (adalimumab, AAA and hs-CRP) were to also be collected just prior to receiving any dose change (blinded therapy, escape to open-label adalimumab, dose de-escalation and dose re escalation).

Study design schematic is provided in Figure 1, Figure 2, Figure 3, and Figure 4. The study activities are summarized in Table 1.

0.6 mg/kg 2.4 mg/kg 1.2 mg/kg 2.4 mg/kg Screening Up to 28 Days Randomization 70-Day Follow-Up Call (max dose (max dose (max dose (max dose of 160 mg) of 160 mg) of 80 mg) of 40 mg) 2.4 mg/kg 1.2 mg/kg 0.6 mg/kg (max dose **PBO** (max dose (max dose of 160 mg) of 80 mg) of 40 mg) Standard dose 0.6 mg/kg (max dose of 40 mg) eow Randomization Stratified by: Responders High dose 0.6 mg/kg Non-Per PMS Corticosteroid used at BL (max dose of 40 mg) ew Responders Prior exposure to anti-TNF BL disease severity Placebo Discontinuation Re-Randomization Stratified by: (70 Days FU) Week 8 remission per PMS **Induction dose**

Figure 1. Study Design Schematic Prior to Amendment 4

DB Induction

DB Maintenance

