Non-responder Imputation (NRI): The NRI approach is used for all binary efficacy variables. These variables can take values of 'Response' (i.e., response, remission or mucosal healing) or 'Non-response' (i.e., non-response, non-remission or no mucosal healing) or may be missing for any reason including discontinuation from study. According to the NRI method all missing values will be considered as 'Non-Response'. Subjects re-randomized due to disease flare will be considered as 'Non-Responders' at and after their 1st re-randomization. The confirmatory efficacy analyses will use NRI approach to impute the missing values.

Additionally, only for sensitivity analyses on the mITT population, a **modified NRI** (**mNRI**) approach to impute the missing values will be used. For mNRI method, subjects re randomized due to disease flare will be considered as 'Non-Responders' at and after the switch to the open-label therapy (2nd disease flare).

Last Observation Carried Forward (LOCF): For categorical and continuous efficacy variables the following rules will be used for LOCF approach:

- Baseline and pre-baseline values will not be used to impute the missing post-baseline values, and
- Missing values after baseline will be imputed using the last non-missing values
 after baseline and prior to the missing value. This includes values from
 unscheduled visits and visits where the measurement was not planned to be
 collected per protocol.
- For subjects who were re-randomized due to disease flare, the last non-missing value before or at the re-randomization after 1st disease flare will be carried forward.

[figure not shown]
Unless otherwise noted, for composite scores which consist of several component subscores, components will be imputed first and the composite score will be calculated based on imputed component subscores. Only if composite score still can't be calculated after imputing component subscores, then the previous composite score will be carried forward. The LOCF analysis will only be performed as sensitivity analysis.

Observed Cases (OC): Observed case analysis will be performed on data until 1st re-randomization of subjects with a disease flare. The following rule will be used: missing values will not be used for the observed case analysis. The OC analysis will only be performed as sensitivity analysis.

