10.6 Efficacy Sensitivity Analyses

[figure not shown]
Sensitivity analyses of the co-primary and ranked secondary endpoints based on OC, mNRI, LOCF and MI (see Section 6.0) will be conducted as applicable. Moreover, the PP population will be used for a sensitivity analysis of the co-primary and ranked secondary endpoints based on NRI.

Additional sensitivity analyses may be performed as deemed appropriate.

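### The maintenance per-protocol set counts major deviations after the first flare re-randomisation, when they can only remove children already fixed as failures

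*SAP*

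**What the plan says.** SAP 5.1 defines two per-protocol sets. For maintenance: "The M-PP population is a subset of the mITT-E population consisting of subjects without major protocol deviations throughout the study". For induction: "The I-PP population is a subset of the ITT-E population/mITT-E population consisting of subjects without major protocol deviations within the induction period". Their role is limited: "The PP populations will only be used for sensitivity analyses of the co-primary and ranked secondary endpoints". The same section makes mITT-E the primary set for the confirmatory maintenance analysis.

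SAP 10.6 adds that "the PP population will be used for a sensitivity analysis of the co-primary and ranked secondary endpoints based on NRI". It does not say which per-protocol set goes with which endpoint.

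The NRI rule in SAP 6.0 is: "Subjects re-randomized due to disease flare will be considered as 'Non-Responders' at and after their 1st re-randomization". Protocol 8.1.4 points the same way for subjects "who receive rescue therapy during the maintenance period will be considered as failures from that time point forward". Re-randomisation is optional after a flare. SAP 4.2 says that "subjects with a disease flare could be re-randomized to receive blinded treatment at or after Week 12".

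Neither document defines a major deviation. Protocol 7.0 lists four reportable types, among them a wrong or incorrect dose and "Subject who received excluded or prohibited concomitant treatment", but does not grade them.

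**The concern.** A per-protocol analysis should leave out children whose deviation could have distorted the outcome being measured. Once a child has been re-randomised for flare, the Week 52 outcome under NRI is settled as a failure, and no later deviation can change it. M-PP nevertheless removes the child for that deviation, so the exclusion falls only on failures.

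The comparison is a one-sample test against a fixed external rate. No concurrent arm loses failures under the same rule, so nothing within the test offsets the effect.

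What is at stake is the value of the per-protocol result as a robustness check on the maintenance co-primary and the ranked secondaries. All of these are binary Week 52 endpoints in Week 8 responders or remitters.

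**Working it through.** **1. Logic of the definitions.** Let m be the number in M-PP and x the NRI successes among them. Let k be the children whose only major deviations come after first re-randomisation.

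- All k are NRI failures (SAP 6.0). An NRI success was never re-randomised, so no success is among the k.
- Rate under SAP 5.1: x/m. Rate if deviations are cut at first re-randomisation: x/(m+k).
- Hence x/m ≥ x/(m+k), with equality only if k=0 or x=0. This holds for the maintenance co-primary and for each ranked secondary within its own denominator.

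**2. The plan's own figure.** Inputs from SAP 4.3: n=57, assumed remission 36%, external placebo 18.37%, two-sided 5%.

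Power = Φ[(|p1−p0|√n − 1.96√(p0(1−p0))) / √(p1(1−p1))] = Φ[(0.1763×7.550 − 1.96×0.3872)/0.48] = Φ(1.19) = 88.3%.

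The stated 88% reproduces, so the test form used below is the plan's.

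**3. Size if k failures leave (k is assumed; the documents give none).** z = (x/n − 0.1837)/√(0.1837×0.8163/n). For simplicity all 57 start in the set, and only post-re-randomisation failures are dropped. The p-values are nominal.

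| Remitters | Dropped | Rate | z | p |
|---|---|---|---|---|
| 16 | 0 | 16/57 = 28.1% | 1.89 | 0.059 |
| 16 | 1 | 16/56 = 28.6% | 1.97 | 0.049 |
| 20 | 0 | 20/57 = 35.1% | 3.26 | 0.0011 |
| 20 | 3 | 20/54 = 37.0% | 3.54 | 0.0004 |
| 20 | 6 | 20/51 = 39.2% | 3.84 | 0.0001 |

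Expressed as an assumed share f of failures dropped, a true rate p appears as p/[p+(1−p)(1−f)]. A true 36% then reads 37.2% (f=5%), 38.5% (10%) or 41.3% (20%).

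Suppose instead that the true rate were 18.37%, with n=57 and each failure dropped independently with probability f. Exact enumeration gives the chance of a significant result in adalimumab's favour as 2.4% (f=0), 4.6% (5%), 5.8% (10%) and 10.9% (20%).

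**4. Net shift against mITT-E.** M-PP also drops remitters with a major deviation. At 36%, dropping k failures is cancelled by dropping k×0.36/0.64 remitters; for k=6 that is about 3.4. In the boundary example, dropping one failure and one remitter gives 15/55 = 27.3%, z = (0.2727−0.1837)/0.0522 = 1.71, p about 0.09. That is below the starting rate.

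**5. Consistency within the SAP.** Maintenance data are cut at first re-randomisation for observed-case and LOCF analyses (6.0), maintenance exposure (9.1) and maintenance adverse events (11.2). M-PP has no such cut.

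**The case against.** A reader might infer that M-PP inflates the adalimumab result, or always moves it in adalimumab's favour. The documents do not support that as a net effect. Remitters spend the full 44 weeks on weekly injections and can also be excluded, so the total movement against mITT-E is open (step 4). That part of the objection stands.

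Other points also stand:

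- With no definition of a major deviation and no deviation rate, k may be zero.
- Several post-flare steps, such as the open-label switch, dose escalation and approved steroid or immunosuppressant changes, are permitted pathways and not deviations. Only errors in carrying them out, or prohibited therapy, would count. That flaring children deviate more often is plausible but is inference.
- The event that fixes failure is the first re-randomisation, which is optional, and not the flare itself.
- I-PP is also described as a subset of mITT-E and counts induction deviations only. If used at Week 52 it would be free of this problem, but SAP 10.6 does not assign it.
- Observed-case, mNRI, LOCF and MI analyses are planned as well, and the per-protocol result supports no formal claim.

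None of this gives a reason to exclude a child for an event that cannot affect that child's endpoint.

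**Conclusion.** The point holds in a limited form. Relative to a set cut at first re-randomisation, the M-PP rate can only be equal or higher for the maintenance co-primary and the four ranked secondaries. This follows from SAP 5.1, 6.0 and 10.6 together, on the assumption that M-PP is the per-protocol set used for the Week 52 endpoints.

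The size is unknown. At the boundary one child is enough to move a nominal p-value across 0.05; at the planned 36% the test is far from the boundary and only the estimate moves. These figures rest on assumed numbers of dropped failures and no dropped remitters.

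The confirmatory mITT-E test, its alpha and the sample size are untouched.

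**What to change.** In SAP 5.1, define M-PP as mITT-E subjects without a major protocol deviation from study start up to the earlier of the Week 52 assessment and the first re-randomisation for flare. State that re-randomised subjects with no earlier major deviation stay in M-PP as non-responders. Report M-PP exclusions by timing (before or after first re-randomisation) and by NRI status, so that the net effect can be seen.

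The cost is a short text change, a date cut in the deviation programming and one extra table. The per-protocol rate may come out slightly less favourable. Re-randomised failures would also be screened for deviations over a shorter window than remitters. That asymmetry is acceptable because deviations outside the window cannot alter the failures' outcome. The change does not settle what counts as a major deviation, which remains a separate gap.
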